6. EFFICACY ANALYSIS

Efficacy results will be summarized for the target mTNBC Population, mBC Population and mUC Population. In addition, selected efficacy data will be summarized separately for each cancer type populations including SCLC, NSCLC, CRC, EGC, EMC and PDC. Formal statistical hypothesis testing will not be performed. Descriptive statistics, data summaries and graphical methods will be used to assess the efficacy of IMMU-132.

The primary endpoint will be the objective response rate (ORR) [PR+CR], with responders requiring a confirmatory response assessment no sooner than 4 weeks after the criteria for response are first met. Assessment of tumor response is based upon on-site readings by local radiologists, using RECIST 1.1 for all populations. Response rates will be additionally provided for the Target mTNBC Population and Per-Protocol Population (specific to mTNBC).

CCI [REDACTED] tumor scans were additionally assessed by independent central review (ICR) for mTNBC patients; however, this is not done for other cancer populations. For mTNBC population, an ICR was conducted for tumor scans from patients who achieved an objective response by local radiologists or at least 20% reduction of their locally determined target lesions. Local vs ICR assessments at each response time point and overall will be compared to determine concordance of local vs ICR best overall results. An imaging scans time point will be presented graphically for the Target mTNBC Population, whether tumor CT scans results were collected within allowed time windows at each of the imaging time points (based on 8 weekly imaging allowed by protocol and collection windows for study time points that were nominally within $\pm 10\%$), based on available data.

Secondary efficacy endpoints will include time to response (TTR), duration of response (DOR), clinical benefit rate (CR+PR+SD [stable disease] ≥ 6 months), progression-free survival (PFS), and overall survival (OS). DOR, PFS, and OS data will be analyzed via Kaplan-Meier method and 95% CI from Brookmeyer and Crowley method with log-log transformation. TTR will be summarized by descriptive statistics, whilst clinical benefit rate will be presented as a response rate along with ORR.

6.1. Best Overall Response

Response will be determined using RECIST 1.1 criteria, and summarized by the best overall response (BOR) using the following hierarchical order: CR, PR, SD, PD, Not evaluable and Not assessed. CR or PR will require a confirmation scan.

6.2. Objective Response Rate

The ORR is defined as the rate of the overall best response as CR or PR. All patients in the applicable analysis population will be included in the denominator in the calculation of the percentage for each response category and ORR. ORR will be summarized by the percentage of responses with 2-sided exact binomial 95% CI.

6.3. Clinical Benefit Rate

Clinical benefit rate (CR+PR+[SD ≥ 6 months]) is defined as those patients with best response as CR or PR or else SD with a duration of at least 6 months. SD for 6 months duration is defined as the time from the first dose to the first documentation of PD or to the last adequate response assessment prior to data cut-off date, whichever is earlier. Clinical benefit rate will be summarized by the percentage of responses with 2-sided exact binomial 95% CI.

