- Blood samples prior to infusion:
 - CBC (with differential and platelet count)
 - Serum chemistry panel (glucose, creatinine, BUN, total bilirubin, AST, ALT, CCI [REDACTED], alkaline phosphatase, serum albumin, total protein, Na, K, calcium, Cl, CO₂, magnesium and phosphorus)
 - PT/PTT [*required only on Day 1 of all even numbered cycles (cycle 2, 4, 6, 8, etc.)*]
- Urinalysis (*required only on Day 1 of all even numbered cycles starting with cycle 2*)
- Physical examination (*required only on Day 1 of all even numbered cycles starting with cycle 2*)
- 12-lead EKG done [*required after completing infusion on Day 1 of all even numbered cycles (cycle 2, 4, 6, 8, etc.)*]
- Concomitant medications (continued, changed)
- Adverse event reporting
- Serum samples for PK analysis: (frozen, to be shipped to Sponsor for analysis). CCI [REDACTED]
[REDACTED]
[REDACTED]

If samples are not collected with the first dose, then all samples should be obtained with the first dose of a subsequent cycle as advised by the Sponsor.

- HAHA sample (frozen, to be shipped to Sponsor for analysis) **CCI** [REDACTED]
- Pregnancy test, if applicable [*required only on Day 1 of all even numbered cycles (cycle 2, 4, 6, 8, etc.)*]

CT or MRI examinations **CCI**

Starting with the initial dose of IMMU-132, **CT or MRI scans** **CCI** [REDACTED] and are to be obtained at 8 week intervals after the first treatment dose until the occurrence of progression of disease requiring discontinuation of further treatment. For scans showing stable disease, but with substantial or rapid tumor shrinkage near threshold for a partial response, the 8-week interval for the next scan may be shortened at investigator discretion and if discussed with the medical monitor. Confirmatory CT/MRI scans are to be obtained in any patient within 4 to 6 weeks of an initial partial response and/or complete response. If a confirmatory scan is performed, then subsequent scans will be scheduled every 8 weeks from the date of confirmatory scan.

Note: MRI abdomen and pelvis with contrast may be done in situations where a CT with contrast is equivocal or contraindicated. A non-contrast chest CT should be done for patients requiring an MRI of the abdomen and pelvis.

CCI

Additional CT or MRI studies may be performed at the discretion of the physician to assess disease status as medically indicated.

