During the study, imaging was performed at baseline (ie, within 4 weeks of study entry) and thereafter in 8 weekly intervals from the start of treatment onwards, with confirmatory CT/MRI scans obtained 4 to 6 weeks after an initial partial response (PR) or complete response (CR), until permanent treatment discontinuation. Response assessment was performed according to Response Evaluation Criteria in Solid Tumors (RECIST) version 1.1. Response assessment was performed locally, but independent central review (ICR) of the tumor scans was additionally obtained for mTNBC patients who had at least 2 prior therapies for metastatic disease, were being treated at the 10 mg/kg dose level, and whose local scans demonstrated at least 20% decrease. ICR of tumor scans was performed by Intrinsic Imaging (Bolton, Massachusetts; San Antonio, Texas, US). The details of the independent review were provided in an imaging charter for the study.

After treatment discontinuation, patients were to be followed until resolution or stabilization of any treatment-related AEs. All patients were followed for survival every month, which may be by telephone with patient or caregiver.

CCI

The safety of patients is assessed based on occurrence of AEs, clinical laboratory assessments, vital signs, and ECGs.

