5.5. Exposure to Study Drug and Compliance

Treatment exposure will be summarized for the Target mTNBC Population, mBC Population, mUC Population and the Overall Safety Population using the following measures:

- Number of doses administered
- Duration of treatment (months)
- Number of patients remaining on the same dose
- Number of IMMU-132 treatment cycles
- Percentage of patients with treatment delays
- Percentage of patients with dose reduction (separately for each category: Any, 1, 2 and 3 dose reductions)
- Time to first dose reduction
- Percentage of patients with permanent treatment discontinuations
- Percentage of patients with infusion interruptions but completed (based on CRF tick box information)
- Percentage of patients with infusions prematurely discontinued (based on CRF tick box information)
- Duration of patient follow-up (from start of treatment to death, last follow up, study discontinuation or data cut-off date)

Duration of treatment (in days) will be calculated as (date of the last dose – date of the first dose + 1) before being converted to months by dividing it by 30.4375. For patients who are still on treatment at the data cut-off date, the date of the last dose will be the latest dosing record end date.

Dose reductions will be calculated by taking the assigned dose level infused for each infusion (from the dose administered CRF). From this it will be possible to calculate when a dose reduction has occurred and the amount by which the dose was reduced. This will enable the dose

reduction, time to dose reduction, and number of patients with a 25% and 50% dose reduction, as outlined above to be derived.

Dose intensity is calculated by the following algorithm:

Delivered dose (in mg) for each infusion is provided per CRF form.

Delivered dosage (in mg/kg) of each infusion in a cycle is calculated by dividing the delivered dose (in mg) by body weight (in kg) at the beginning of the cycle (the body weight according to which the prescribed dose is calculated and prepared per the Protocol).

Cumulative dosage (in mg/kg) received for each subject is defined as the sum of all delivered dosage (in mg/kg) of all infusions the subject received in the study.

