If the onset of response required evaluations at different times (ie, chest CT on 1 day, abdomen and pelvic MRI several days later) the last measurement date was to be used. For PD based on the sum of target lesion measurements at different times, the last measurement date was to be used. For PD based on new or non-target lesions, if these were equivocal at 1 assessment and later considered unequivocal PD, the earliest date when progression was suspected was to be used.

¹ *Adequate response assessment was defined as a response assessment other than 'not assessed' or 'not evaluable'. As progression was based on the sum of target lesion measurements at different time points, the last measurement date was to be used. For progression based on new or non-target lesions which were equivocal at 1 assessment but later considered unequivocal PD, the earliest date when progression was suspected was to be used.*

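### Clinical benefit times stable disease to the PD scan in progressors but to the last scan in everyone else, against a 6-month cut that falls between the week-24 and week-32 scans

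*SAP*

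**What the plan says.** SAP section 6.3 defines clinical benefit as patients "with best response as CR or PR or else SD with a duration of at least 6 months". The duration rule that follows has two end points. The first is progression: "SD for 6 months duration is defined as the time from the first dose to the first documentation of PD". The second is the "last adequate response assessment prior to data cut-off date, whichever is earlier".

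The footnote to SAP Table 3 says what adequate means: "Adequate response assessment was defined as a response assessment other than 'not assessed' or 'not evaluable". SAP section 6.6 repeats that definition for duration of response. Section 6.3 does not restate it.

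Protocol section 6.4 says that scans "are to be obtained at 8 week intervals after the first treatment dose", and SAP section 3.1 has them "thereafter in 8 weekly intervals from the start of treatment onwards". SAP section 6 mentions "collection windows for study time points that were nominally within" ±10%, without saying 10% of what.

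SAP Table 3 censors PFS at the last adequate assessment before the gap when PD follows two or more missed assessments. It also censors when other treatment starts. Section 6.3 has neither rule. Clinical benefit rate (CBR) is a secondary endpoint, reported with an exact 95% CI.

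**The concern.** A rule for SD duration should give the same answer to patients with the same evidence of stability. This one need not. The two end points differ by up to a full scan interval, and the 6-month cut sits inside such an interval. Around week 24, a patient's classification can therefore turn on whether a later PD scan was obtained, and the patient known to have progressed is the one credited.

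The missing gap rule adds a second anomaly: a patient can have SD of at least 6 months for clinical benefit while the SAP's PFS rule accepts stability only to week 8.

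At stake is the meaning of CBR and its CI in the Target mTNBC Population and in the mBC, mUC and six other cancer populations for which SAP Table 2 lists it.

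**Working it through.** **Inputs**
- Scans at weeks 8, 16, 24 and 32 from first dose (protocol section 6.4, SAP section 3.1).
- Month length 30.4375 days. SAP section 5.5 gives treatment duration in days "before being converted to months by dividing it by 30.4375", and sections 6.4 and 6.6 use the same divisor for PFS and DOR. Section 6.3 states none, so its use here is an assumption.
- Target mTNBC Population N = 108 (SAP section 4).
- The SAP states no expected CBR, so there is no planned figure to reproduce.

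**Step 1: where the cut falls**
- 6 months = 6 × 30.4375 = 182.6 days.
- Week 24 = 24 × 7 = 168 days; 168 / 30.4375 = 5.52 months.
- Week 32 = 32 × 7 = 224 days; 224 / 30.4375 = 7.36 months.
- Adding one day, as the PFS formula does, gives 5.55 and 7.39 months. The cut stays between the scans.

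**Step 2: what the earlier-of-two clause does**

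A PD scan is neither not assessed nor not evaluable, so it is itself an adequate assessment. For a progressor, the last adequate assessment is therefore the PD scan or a later one. The clause never moves the end point back to the last SD scan.

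**Step 3: three patients under section 6.3**

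| Scans | End point used | SD duration | Clinical benefit |
|---|---|---|---|
| SD at weeks 8, 16, 24; PD at week 32 | PD scan, day 224 | 7.36 months | Yes |
| SD at weeks 8, 16, 24; no later adequate scan | Week-24 scan, day 168 | 5.52 months | No |
| SD at week 8; weeks 16 and 24 missed; PD at week 32 | PD scan, day 224 | 7.36 months | Yes |

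The first two have identical SD scans. For the third, Table 3 censors PFS at week 8: 56 / 30.4375 = 1.84 months (1.87 with the extra day).

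**Step 4: can the visit window close the gap?**
- 10% of the 8-week interval: 0.10 × 56 = 5.6 days. Week 24 then spans 162.4 to 173.6 days, or 5.34 to 5.70 months, and never reaches 6.
- 10% of elapsed time: 0.10 × 168 = 16.8 days. Week 24 then spans 151.2 to 184.8 days, or 4.97 to 6.07 months, and reaches 6 only in about its last two days.
- Week 32 is at least 6.62 months on either reading (0.90 × 224 = 201.6 days).

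**Step 5: size**

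One patient is 1/108 = 0.93 points. The documents do not give the number affected. If it were 1, 3, 5 or 10, the shift would be 0.9, 2.8, 4.6 or 9.3 points. As an illustration with an assumed base, 40/108 = 37.0% (exact 95% CI 27.9 to 46.9) becomes 45/108 = 41.7% (32.3 to 51.5) when five patients are reclassified.

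**The case against.** The strongest reply is that section 6.3 follows the protocol. Appendix 4 measures SD from the start of treatment until the progression criteria are met, and PFS uses the same pattern: the PD date if there is one, the last adequate assessment if not. That stands. Timing SD to progression is a recognised convention, and a reader who inferred that section 6.3 is simply an error would be going too far. The convention does not justify pairing the two end points with a fixed cut between scans, because CBR is a yes/no classification and cannot carry censoring as a Kaplan-Meier estimate does.

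A reader might also infer that CBR is understated. The documents do not support that. A patient last seen stable on day 168 has 5.52 months of documented SD, and excluding that patient is a conservative reading of a 6-month threshold. Ending SD at the last non-PD scan for everyone would be equally consistent; neither of the first two patients would then count, and CBR would fall.

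A third tempting reading is that PD on a late week-24 scan, at day 183 or 184, would pass. That needs the 10% to apply to elapsed time, which the documents do not say.

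The affected group is also limited. Protocol section 6.7 asks for scans every 3 months in patients who have not progressed, until PD or other treatment, for up to 2 years. The planned final cut-off of 1 March 2019 is 617 days (20.3 months) after the last enrollment on 22 June 2017, so the cut-off itself cannot produce the second patient in the table. Loss to follow-up, withdrawal, new therapy or death without a PD scan still can.

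Finally, CBR is secondary and descriptive, with no hypothesis test. SAP Table 1 does not list it among the mTNBC efficacy outputs, although section 6 names it without restricting the population. Programming rules sit in a separate document, which may address some of this.

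**Conclusion.** The inconsistency is real and follows from the SAP's own text. Patients with the same SD scans are classified differently according to whether a PD scan follows, and a patient whose PFS is censored at week 8 can count as having 6 months of SD.

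This rests on two assumptions: that the 30.4375-day month applies in section 6.3, and that adequate has the meaning given in Table 3 and section 6.6. If 6 months was meant as 24 weeks, the first anomaly largely disappears; the missed-scan anomaly does not.

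The number of patients affected and the net direction cannot be determined from the documents. Each patient is worth 0.93 points at N = 108, and more in a smaller cohort. ORR is unaffected. This is a cheap improvement to a secondary descriptive endpoint, not a flaw that undermines the trial's main result.

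**What to change.** In SAP section 6.3, count SD as clinical benefit for all patients, progressed or not, only when at least one adequate non-PD assessment is obtained at or after the week-24 visit and before any other anticancer treatment. In addition:
- State the base of the window. With 10% of the 8-week interval, the visit opens at 168 − 5.6 = 162.4, in practice from day 162. Under an elapsed-time base it would open near day 151 (4.97 months), so this cannot be left implicit.
- Where a confirmatory scan has reset the schedule (for example weeks 20 to 22, then 28 to 30), apply the rule by study day rather than visit label.
- Report the existing 6-month calculation alongside, for continuity. SAP section 9 records that earlier administrative analyses were done, so a changed definition should not simply replace the old one.

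Under this rule the first two patients in the table both count and the third does not.

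The cost is a short rewording of section 6.3, a derivation change and one extra output. The downsides are that the cut becomes 24 weeks rather than 6 calendar months, that it departs from the Appendix 4 convention of timing SD to progression, and that patients on a reset schedule are still judged at a somewhat different time from the rest.

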6.4. Progression-Free Survival

Progression-free survival is defined as the interval from the first dose start date to the date of disease progression defined as documented PD or death from any cause, whichever occurs first. Death was considered an end point only while the patient was on study and receiving treatment or undergoing response assessments. Patients otherwise without adequate response assessments or without radiologic evidence of progression were censored. Clinical PD was not considered as a PFS event. $PFS = (\text{Earliest Date of Disease Progression/ Death} - \text{First Dose Start Date} + 1) / 30.4375$.

The approach regarding handling of assessments, dates, and censoring presented in [Table 3](#) is based upon RECIST1.1 guidelines ([Eisenhauer et al., EJC, 2009](#)). **CCI**

[figure not shown]

Table 3: Guidelines for Response Assessment and Censoring for Analysis of Progression-Free Survival

Guidelines for Progression Assessment and Censoring for Analysis of PFS		
Case	Outcome	Date of Event/Censoring¹
No adequate response assessment after start of treatment		
Died prior to second scheduled assessment	PD	Date of death
Did not die prior to second scheduled assessment	Censor	Date of first dose
Continued study until objective PD or death		
At scheduled assessment	PD	Date of objective PD
Between scheduled assessments	PD	Date of objective PD or death
After missing 2 or more scheduled assessments	Censor	Date of last adequate response assessment before missed ones
Continued scheduled response assessments without objective PD or death		
Discontinued for undocumented PD, toxicity, other reasons	Censor	Date of last adequate response assessment
Lost to follow-up	Censor	Date of last adequate response assessment
Initiated other treatment	Censor	Date of last adequate response assessment prior to starting other treatment
No objective PD at final assessment	Censor	Date of last adequate response assessment

Abbreviations: CT = Computed tomography, MRI = Magnetic resonance imaging, PD = Progressive disease, PFS = Progression-free survival.

If the onset of response required evaluations at different times (ie, chest CT on 1 day, abdomen and pelvic MRI several days later) the last measurement date was to be used. For PD based on the sum of target lesion measurements at different times, the last measurement date was to be used. For PD based on new or non-target lesions, if these were equivocal at 1 assessment and later considered unequivocal PD, the earliest date when progression was suspected was to be used.

¹ *Adequate response assessment was defined as a response assessment other than 'not assessed' or 'not evaluable'. As progression was based on the sum of target lesion measurements at different time points, the last measurement date was to be used. For progression based on new or non-target lesions which were equivocal at 1 assessment but later considered unequivocal PD, the earliest date when progression was suspected was to be used.*

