Starting with the initial dose of IMMU-132, CT (or MRI if needed) examinations are to be obtained at 8-week intervals until the occurrence of progression of disease requiring discontinuation of further treatment. For scans showing stable disease, but with substantial or rapid tumor shrinkage near threshold for a partial response, the 8-week interval for the next scan may be shortened at investigator discretion and if discussed with the medical monitor. Confirmatory CT/MRI scans are to be obtained 4 to 6 weeks after an initial partial response and/or 4 to 6 weeks after an initial complete response. If a confirmatory scan is performed the subsequent scans will be scheduled every 8 weeks from the confirmatory scan. Tumor biomarkers are to be obtained at the time of radiologic evaluations. **CCI**

After discontinuing treatment, the patient will undergo an end-of-study evaluation, with additional follow-up only required until resolution or stabilization of any treatment-related toxicity. Additional CT or MRI may be performed at the discretion of the physician to assess disease status as medically indicated.

Long-term follow-up will continue in patients with stable disease or an objective response with evaluations performed every 3 months for up to 2 years or until progression of disease or initiation of other treatment. All patients will be followed every month for survival, which may be by telephone, for no longer than 2 years from final study evaluation.

Patients continuing to benefit from treatment at time of study closure may be eligible to enroll in a rollover study, so they may continue to receive treatment.

(See study calendar for detailed schedule of study procedures)

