6.8. Criteria for Removal from Protocol Treatment

Patients may be removed from protocol treatment under the following conditions:

- First documentation of progressive disease (Physician discretion and Sponsor approval to continue) or symptomatic deterioration indicating treatment failure.
- Patients who want to continue treatment after radiological documentation of progressive disease should notify the physician who will obtain Sponsor approval before treatment continuation.
- Unacceptable toxicity.
- Treatment delay for any reason > 3 weeks (Treatment delays of up to 3 weeks will be allowed at the investigator's discretion).
- The patient may withdraw from the study at any time for any reason.

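### SAP 6.4 gives conflicting rules on which deaths are PFS events, so deaths soon after withdrawal for undocumented progression can be censored, which is expected to bias PFS upward by an unknown amount

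*SAP*

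**What the plan says.** SAP 6.4 takes as the event "documented PD or death from any cause, whichever occurs first". The sentence after it narrows this: "Death was considered an end point only while the patient was on study and receiving treatment or undergoing response assessments". The same paragraph adds: "Clinical PD was not considered as a PFS event".

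Three rows of Table 3 matter:

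- With no adequate assessment after the start of treatment, a death before the second scheduled assessment is an event on its date. Being on treatment is not required.
- A death between scheduled assessments is an event, within the block for patients who stay on study until progression or death. It is censored if two or more assessments were missed.
- "Discontinued for undocumented PD, toxicity, other reasons" is censored at the last adequate assessment.

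On who is still being imaged, SAP 3.1 describes 8-weekly scans "until permanent treatment discontinuation". Protocol 3 says that after treatment there is an end-of-study evaluation "with additional follow-up only required until resolution or stabilization of any treatment-related toxicity". Its next paragraph, and Protocol 6.7, continue 3-monthly evaluations for up to 2 years in patients who have not progressed.

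Protocol 6.8 lists "symptomatic deterioration indicating treatment failure" as a ground for removal from treatment. Appendix 4 asks sites to try to document objective progression in such patients even after they stop. All patients have monthly survival follow-up. Protocol 10.4 puts no limit on death in PFS.

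**The concern.** The restricting sentence contradicts the definition just before it, and it conflicts with the early-death row of Table 3. Its key phrase, undergoing response assessments, has no readable definition or time window. Two analysts could code the same patient differently.

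The patients at issue are not a random subset. They stopped because they were failing, clinical progression is not an event, and death is the only remaining evidence of failure if no further scan is done. Censoring them at the last scan assumes that they had the same outlook as patients who stayed under assessment.

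PFS is a secondary endpoint for nine populations (SAP 5 and 6). There is no control arm, so the curve is read on its own. Sensitivity analyses are confined to the Target mTNBC Population (SAP 4.1 and 6.9), so in the other eight the rule stands alone.

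**Working it through.** **The rules side by side.** Two illustrative patients, with times from the SAP formula (days + 1) / 30.4375.

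Patient A has stable disease at week 8, stops at week 12 for symptomatic deterioration, has no further scan, and dies at week 15.

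| Rule applied | Outcome for A |
|---|---|
| Definition (any-cause death) | Event, week 15: (105 + 1) / 30.4375 = 3.48 months |
| Restricting sentence, imaging as in SAP 3.1 | Censored, week 8: (56 + 1) / 30.4375 = 1.87 months |
| Restricting sentence, imaging as in Protocol 6.7 | Arguably still under assessment: event, week 15 |
| Table 3, undocumented-progression row | Censored, week 8 |
| Table 3, between-assessments row | Event, week 15, if A counts as having continued on study |

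Patient B has no adequate post-baseline scan, stops at week 5 and dies at week 10. The second scheduled assessment is at 2 × 8 = 16 weeks. Table 3 makes B an event at (70 + 1) / 30.4375 = 2.33 months. The restricting sentence, read with SAP 3.1, discards the death.

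**Size.** The readable text gives no assumed PFS median, event count or rate of undocumented withdrawal, so there is no plan figure to reproduce. Direction and size were explored by Kaplan-Meier simulation with 100,000 patients per scenario. The 8-week scan interval is from the protocol. The following inputs are assumptions:

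- exponential time to progression, median 4 or 6 months;
- 5%, 10%, 20% or 30% of patients withdrawn at progression without a documenting scan and never scanned again;
- exponential time from withdrawal to death, median 1, 2, 4 or 8 months.

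This gives 2 × 4 × 4 = 32 scenarios. Four rules were compared: the restricting sentence taken literally; the same with the early-death row of Table 3; deaths counted unless two or more 8-weekly scans were missed; and every death counted.

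6-month PFS (%), progression median 4 months:

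| Withdrawn | Median to death | Literal | With early-death row | Fewer than 2 missed | All deaths |
|---|---|---|---|---|---|
| 5% | 1 month | 40.0 | 39.6 | 38.8 | 38.8 |
| 10% | 1 month | 41.8 | 40.8 | 39.2 | 39.3 |
| 20% | 1 month | 45.2 | 43.0 | 39.8 | 39.9 |
| 30% | 1 month | 49.7 | 46.1 | 40.8 | 40.9 |
| 20% | 8 months | 45.7 | 45.1 | 44.3 | 47.7 |

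- Against the fewer-than-two-missed rule, the literal sentence was higher in all 32 scenarios, by 0.3 to 8.9 points at 6 months. With the early-death row the excess was 0.2 to 5.3 points. A recheck that let the missed-assessment limit after withdrawal run to two 3-monthly scans gave the same direction throughout.
- Against counting every death, with a median of 1 to 2 months to death, the excess was 0.6 to 8.8 points (literal) or 0.3 to 5.2 points (with the early-death row).
- With a median of 8 months to death, the figure with the early-death row was 0.3 to 3.3 points lower than counting every death.
- In the 20%, 1-month case the early-death row cuts the excess over all deaths from 45.2 − 39.9 = 5.3 to 43.0 − 39.9 = 3.1 points, which removes 2.2 / 5.3, about 40%.
- The median is a poor gauge, because progression falls on the scan grid. It stayed at 5.52 months under the first three rules in every scenario with a 4-month progression median. With a 6-month median it either did not move or jumped a whole scan interval, from 7.36 to 9.20 months.

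**The case against.** A reader might infer that every patient withdrawn for deterioration who then dies is censored, and that PFS is therefore overstated. The documents do not support that. Table 3 counts some early deaths. Protocol 6.7 keeps imaging patients who have not progressed, and Appendix 4 asks for progression to be documented after treatment stops. A patient such as A may thus still be under assessment, and the restricting sentence would then count the death. Only the SAP 3.1 summary points the other way. The SAP also cites the protocol as of Amendment 11, whereas the protocol reviewed includes Amendments 12 and 13.

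A reader might also infer that such censoring always lengthens PFS. It need not: censoring at an earlier scan shrinks the risk set, and when deaths come late the estimate can fall below one that counts every death.

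The magnitude rests wholly on assumed inputs. Text beside Table 3 and in SAP 6.9 and 11 is redacted, so a mitigating analysis may exist. PFS is secondary, no hypothesis is tested, ORR is primary, and OS counts all deaths.

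All of this stands, and it limits the claim. It does not remove the conflict between the definition, the sentence after it and Table 3. The uncertainty over imaging after treatment is itself a reason to write one rule.

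**Conclusion.** SAP 6.4 is wrong as written, because its definition, its restricting sentence and Table 3 do not give one answer on which deaths are PFS events. Patients withdrawn for undocumented or symptomatic progression who die soon afterwards can be censored although the death is on file. That censoring is informative and is expected to bias PFS upward.

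The size cannot be derived from the documents. The simulated 0.3 to 8.9 points at 6 months assumes 5% to 30% of patients so withdrawn and none scanned again. Continued imaging under Protocol 6.7 would reduce it. For scale, with 108 patients in the Target mTNBC Population and 6-month PFS near 40%, a rough 95% half-width ignoring censoring is 1.96 × √(0.40 × 0.60 / 108) = 9.2 points. The bias could thus be negligible or close to the sampling error.

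This should be fixed. It is not critical, since the endpoint is secondary and descriptive, there is no type I error or power consequence, and ORR and OS do not change.

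**What to change.** 1. Delete the restricting sentence. State that death from any cause is a PFS event on its date, whether or not the patient is on treatment, except after other treatment was started or after two or more missed scheduled assessments.
2. Count missed assessments on the protocol schedule: 8-weekly on treatment and 3-monthly afterwards under Protocol 6.7. Without this, a patient with no scans scheduled can never miss one, and very late deaths would become events. Reconcile the imaging description in SAP 3.1 with Protocol 6.7.
3. Limit the Table 3 row for discontinuation with undocumented progression, toxicity or other reasons to patients with no later death that meets rule 1.
4. Add a sensitivity analysis counting all deaths as PFS events, unless redacted text already contains one.
5. Align duration of response: Table 4 counts death as an event, while its note censors patients who died without objective progression.

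The cost is SAP wording and a rerun on data already held; PFS may be slightly shorter. Because data to the 30 June 2017 cut-off were already analysed under SAP version 2.0, SAP 11 should record the change as made after that analysis.
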